8. STUDY-WIDE RECRUITMENT METHODS*

N/A

9. STUDY TIMELINES*

Phase I of the Project was completed within the 1st year of the project (technically within 6 months of the Phase 1 notice of award), and Phase 2 tasks will be completed within years 2 and 3 of the project. See grant: "PROJECT TIMELINE" (p.16) for details.

10. STUDY ENDPOINTS*

See grant: "RESEARCH STRATEGY" (p.11-13) for details.

11. PROCEDURES INVOLVED*

Measures: For Phase 1, the System Usability Scale (SUS) (patients and clinicians), Timeline Followback (TLFB) (patients only), and Addiction Severity Index (ASI) (patients only) will be used and is included in this submission. For Phase 2, The Mini Quiz (MQ), Mini-Usability Acceptability Testing (Mini-UAT) questionnaire, Timeline Followback (TLFB), PROMIS Pain Intensity and Interference Scales (PIIS), HIV Risk Behavioral Scale (HRBS), Post-traumatic Stress Diagnostic Scale for DSM-5 (PDS), Treatment Satisfaction Scale (TSS), and the System Usability Scale (SUS) will be used and are included in this submission.

Assessments/Procedures for Phase 2	Intake	Onboarding	Transition to Suboxone	Week 1 to 12	Month 1	Month 3 / End of Tx	Month 6
Mini Quiz, Patient form, OUD	X						
Mini-UAT, Service Utilization, TLFB	X				Х	Х	Х
PIIS, HRBS, PDS, U-Tox	X				Х	Х	Х
Healthcare Utilization	X						Х
App training, warm hand-off scheduling outpatient Suboxone intake		Х					
Monitor completion of MOUD intake			Х				
MOUD TAU / OARS+CM				Х			
Monitor treatment attendance/u-tox				X			
Treatment satisfaction, SUS*						Х	

^{*}Only for OAR+CM group

Phase 1: Aim 1 (Develop OARSCM): 30 Clinicians (20 user testing, 10 dyads) and 30 Patients

- 1a. After the OARSCM is developed, patients meeting criteria and consenting to participate will be guided through using the mobile application on their personal smartphone. If the participant's smartphone is not available for use to complete the instructed tasks, the participant will be able to use a study-provided iPad.
- 1b. Clinicians not associated with a specific patient participant verbally consenting to participate after reviewing the User Testing Fact Sheet will be guided through using the provider portal using a test account on a study provided computer in a private office.
- 1c. Clinicians working at the UMass Bridge Clinic, at the CleanSlate Addiction Treatment Center at SaVida Health, and at Spectrum Health Systems associated with a patient participant (considered a dyad) verbally consenting to participate after reviewing the Dyad Fact Sheet will receive an in-person or virtual training on the provider portal on a study provided computer in a private office. After the training, the clinician will provide standard MAT treatment to patient participants and use the OARSCM provider portal to track treatment.
- 2a. Patient participants will complete a short survey on the iPad and a 20-30-minute interview-assessment during their hospital visit. Patient will provide their general impressions of the OARSCM mobile application (e.g., perceived appropriateness, acceptability, and feasibility), as well as any identified barriers or weaknesses. It will not interfere with care.
- 2b. At a later time, all clinicians (dyad or not) will complete an in-person or virtual interview to provide their general impressions of the OARSCM provider portal (e.g., perceived appropriateness, acceptability and feasibility), as well as any identified barriers or weaknesses. This clinician interview will occur outside of the acute care and outpatient visit to not interfere with any patient care. All interviews will be audio recorded with verbal consent.
- 3. If a dyad clinician elects to withdraw from the study but the patient chooses to remain enrolled, a research assistant will be responsible for inputting the patient data into OARSCM as to not interrupt the patient's ability to earn prizes. We would also not obtain the clinician's user testing data.
- 4. Patient will be connected to a community based Suboxone treatment provider, the UMass Bridging Clinic, the CleanSlate Addiction Treatment Center, SaVida Health, or Spectrum Health Systems and schedule an intake appointment. Patient will receive standard MAT treatment and will use the OARSCM mobile application to track their progress in treatment. To use the OARSCM mobile application to track their progress in treatment, patient will enter their name (first and last), email address, DOB and cell phone number when available into the application to create an account. Patient will have the option to journal free text entries about how they are thinking and feeling throughout treatment. Patient will have the opportunity to earn prizes for engaging the OARSCM program throughout treatment. Engagement in treatment is measured by scheduling and attending treatment appointments as well as urinary tox results, all of which is entered into the OARSCM program by the MAT provider using the provider portal. See "APPENDIX" for screenshots of patient application and provider portal.

5. Patient will not receive any follow up calls after the hospital visit but will have their use of the OARSCM mobile application and engagement with treatment as tracked by the OARSCM mobile application monitored for 4 weeks. Participation in this study will last about 4 weeks once the patient has started MAT treatment. After these 4 weeks, the participants will be informed that their 4-week participation has now ended and that we appreciate their participation. They will also be informed that new information related to their appointments, appointment attendance, appointment engagement and tox results will not be entered into their OARSCM mobile application profile. However, they will be able to view this DATA that had been previously entered throughout the 4-weeks. They will continue to have access to their OARSCM mobile application account in order to use their unredeemed Spins, Prizes, and eGift cards for a short time. During enrollment, patient participants will be given a handout on how to uninstall the application if they no longer want the application on their smart phone after participation. See grant: "RESEARCH STRATEGY" (p. 8). See grant: "APPENDIX" for screenshot of patient notification that their 4-week participation has now ended and handout of how to uninstall the mobile application.

Phase 2: Aims 1 and 2 (Efficacy of OARSCM): 102 patients randomized to 1 of 2 groups If the patient agrees to participate:

- 1. Participants (acute care patients who meet eligibility criteria and complete consent process, see section 30. Consent Process) will be randomized to either TAU (with MyMAT) or OARS mobile application plus contingency management (OARSCM).
- 2. Participants will complete an interview assessment during their current medical visit. It takes about 20-30 minutes to complete. They will be asked to provide a urine sample. It will not interfere with their care.
- 3. Participants will be provided a warm handoff to a community-based MOUD treatment provider. All participants will be eligible to receive standard MOUD treatment per treatment as usual at the site they are referred to. If they are randomized to OARSCM, they will use the mobile application to track treatment progress and have the potential to earn prizes for engaging with the application throughout treatment.
- 4. Participants will receive a welcome call at 1-week post-enrollment. This call will welcome participants to the study and provide an opportunity to answer any questions they may have about participation as well as ensure they are not having any issues with study mobile applications. This call will take about 5 minutes.
- 5. They will complete 3 follow-up telephone calls to find out how they are doing. The calls will focus on their substance use, especially opioid use, treatment engagement, healthcare visits, health, and well-being. These calls will take about 20 30 minutes to complete. The calls will occur at 1, 3, and 6 months after the enrollment date.
- 6. The researchers will review the participants' healthcare records, including the Massachusetts Prescription Monitoring Program's EHR-integrated tool MassPAT that provides information on participant's prescriptions for MOUD through the 6 months after enrollment. We will review the

healthcare record for all participants and will only be viewing the MassPAT record for participants who do not have urine toxicity results at their outpatient MOUD provider at the 1, 3, and 6-month follow up time points. MassPAT will be used to determine if a participant is still engaging in treatment during these follow-up time points if the participant cannot be reached for their follow-up interviews or if they have stopped attending appointments at their study clinic site and have not requested to leave the study.

- 7. We will be seeking to collect information from medical providers or records outside of the UMMS system (a substance use treatment provider in the community that doesn't have a UMMS connection) and will require a signature on a Release of Medical Information with designated treatment facilities identified
- 8. The researchers will review publicly available databases, like the participants' state's vital statistics registry (a document created by the state that tracks important health indicators, like births, deaths, and cause of death). See grant: "RESEARCH STRATEGY" (p.8-13) for details.

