5. BACKGROUND*

See grant: "RESEARCH STRATEGY" (p.2-4) for details. The Procedures for Phase 2 have been modified from the original submission. Updated Procedures are as follows:

Procedures

Screening, recruitment, eligibility and training procedures are in C.2.1 and the Eligibility criteria document.

Randomization will occur following determination of eligibility using an urn procedure and stratifying on 1) other (than opioid) substance use disorder no/yes, 2) gender/sex, 3) race/ethnicity.

TAU with MyMAT (n = 51). In the acute care setting, the Behavioral Health Service run by Drs. [name] and [name] provides SBIRT for substance use disorders, including OUD. They provide SBIRT as part of TAU, including, when possible, warm handoff contact with outpatient MOUD treatment that includes a scheduled outpatient appointment, optimally within 48 hours of the ED visit. Patients randomized to this group will also receive MyMAT, a mobile application with opioid treatment educational content, as an attention control measure against OARS+CM. TAU outpatient suboxone treatment consists of urine toxicology screening, group/individual therapy, and MOUD prescription continent on drugnegative (except cannabis, which is legal in MA) urine toxicology. Treatment visits are typically, weekly in weeks 1-4 and then taper over time, to every other week in weeks 5-8, and monthly in weeks 9-12 and thereafter. Nonadherence can lead to increased frequency/intensity of therapy and urine toxicology until the patient stabilizes. If increased frequency/intensity is unsuccessful, patients may be referred to detoxification and subsequently re-admitted to outpatient care when appropriate.

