23. RESOURCES AVAILABLE

Research Personnel. Investigators and key personnel will have undergone mandatory education in human research participants' protection. Educational systems are in place to ensure that all research staff have been through such training and are approved by the IRB Human Subjects department. The responsibilities of investigators and research personnel are as follows:

Principal Investigator. The Principal Investigator will be responsible for overall project governance at UMass, leadership of the Project Team at UMass, protocol development, informing the data analytic plan, and dissemination efforts through professional presentations and peer reviewed journal publications

Co-Investigator. The Co-Investigators will be responsible for collaboration with other MOUD providers in the region and overseeing communication between research staff and community MOUD providers. Other responsibilities include overseeing contingency

management plan development and implementation and advising the team on data management and quality assurance protocols.

Project Manager. The Project Manager will be responsible for managing daily operations of recruitment and enrollment including training and supervising the research assistants. They will manage all IRB related submissions, amendments, and reporting.

Research Assistant(s). The research assistant(s) will be responsible for reviewing the electronic health record dashboard each shift and documenting potentially eligible patients on a Screening Log. They will be responsible for enrolling participants conducting interviews and completing telephone outcome assessment services for the stud(ies).

Software Engineer. The software engineer will be responsible for programming and managing the OARSCM mobile application and ensuring all data is flowing correctly between the mobile application and the secure server. They will have access to identified data within the Q2i OARSCM secure server at AWS. This data will include the patient's name (first and last), DOB, email address, cell phone number, urine toxicology results, and attendance in treatment. PHI will be directly entered into the mobile application. Q2i will have access to the server via secure shell terminal sessions. The OARSCM mobile application does not store PII/PHI locally on the device.

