Phase 2 Aims 1 & 2 (RCT of OARSCM): Patients will complete a screening survey to assess for minimal eligibility criteria and confirm their interest. If a potential participant is deemed ineligible for the study, they will be informed that they are not a good fit for this study and the screening form will be shredded immediately after the encounter. After the RA consents the participant, they will open a randomization envelope and randomize the patient to either TAU or OARSCM. For TAU the participant will receive SBIRT provided by the RA, a warm handoff to a community MOUD treatment facility and will be trained on how to use MyMAT (an educational mobile application). For OARSCM the participant will receive TAU as described

above with the addition of the OARSCM mobile application instead of MyMAT. Participants will be trained on how to use the OARSCM mobile application, potentially earning prizes throughout treatment as part of contingency management. After leaving the ED, participants will complete follow-up calls at 1, 3, and 6-month time periods.

In Phase 2, all participants will receive an initial \$25 remuneration for enrollment during their ED visit, an additional \$30 per follow-up call (1 and 3 months), and an additional \$35 for completing the 6-month follow-up call for a total of \$120/participant. Those randomized to the contingency management group have to opportunity to earn additional money as part of treatment. See grant: "RESEARCH STRATEGY" (p12) "Procedures" for further details.

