Phase 2, RCT. will proceed with the intent-to-treat sample. Initial analyses will compare groups on baseline and demographic variables using chi-square test (for categorical variables) and analysis of variance (for continuous variables). Variables that significantly differ between groups or are theoretically important, such as pain and other (non-opioid) substance use disorder will be used as covariates in multivariate analysis, when appropriate. For end-of-treatment outcomes, analysis will compare groups via chi-square, Kruskal-Wallis test, and analysis of variance (ANOVA) or analysis of covariance (ANCOVA) tests, as appropriate. Evaluation of changes in outcomes through the follow-up period will occur with hierarchical mixed models specified for dichotomous or continuous outcomes. To use the mixed effect modeling analysis in assessing intervention effect, an interaction term (intervention group by time) will be included together with other covariates (e.g., age, ethnicity, chronic pain, anxiety, trauma history, utilization of psychiatric or medical services). A significant beta coefficient of the interaction term at $p < .05$ level will be used as evidence supporting the intervention effect. Analysis of change scores can analyze variables that cannot be normalized.

The Primary Aim 1 is to assess the efficacy of OARS+CM in promoting Suboxone treatment initiation.

The primary outcomes will be the proportion of participants who schedule a Suboxone treatment intake visit, and the proportion of participants who complete the Suboxone intake visit to start outpatient treatment. These outcomes are usually non-normally distributed and will be analyzed accordingly. We will assess the effect of the intervention using generalized linear mixed model, controlling for the dependence of repeated measures and the clustering effects.

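### The Phase 2 steps place randomisation before the baseline interview, so self-reported covariates may be collected with the arm known

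*Protocol*

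**What the plan says.** Protocol Section 11 (Phase 2, Aims 1 and 2) gives a numbered list. Step 1 randomises patients who are eligible and have consented. Step 2 is the 20 to 30 minute baseline assessment, "Participants will complete an interview assessment during their current medical visit", with a urine sample. Step 3 is the warm handoff.

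Section 24 describes enrolment again: "After the RA consents the participant, they will open a randomization envelope and randomize the patient to either TAU or OARSCM". Arm-specific procedures and app training follow. The baseline interview is not mentioned.

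Section 5 ties allocation to eligibility and names the first stratifier: "Randomization will occur following determination of eligibility using an urn procedure and stratifying on 1) other (than opioid) substance use disorder no/yes". Sex and race/ethnicity are the other two.

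Section 23 describes the research assistants' duties: "They will be responsible for enrolling participants conducting interviews and completing telephone outcome assessment services". By Section 24 the same role opens the envelope and delivers the SBIRT in the TAU arm. No blinding of interviewer or participant is described.

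The assessment table in Section 11 lists TLFB, service utilisation, pain, HIV risk, PTSD and urine toxicology under Intake.

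The SAP gives example covariates for the mixed models: "age, ethnicity, chronic pain, anxiety, trauma history, utilization of psychiatric or medical services". It also adjusts for variables that differ significantly between arms at baseline, and it allows change scores.

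**The concern.** A baseline covariate is safe to adjust for because allocation cannot have influenced it. That protection weakens if the participant, or the person asking the questions, already knows the arm. One arm can win prizes for opioid-negative urine tests and for attendance; the other receives an educational app. Answers about recent use, pain, trauma or service use could differ by arm for that reason alone, although the documents give no basis for predicting the direction.

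The SAP's selection rule makes this worse. A reporting difference produced by allocation looks like a chance imbalance, and the rule then brings that variable into the model as a covariate. In a change score the baseline shift enters directly.

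There is also a missing-data route. A participant who leaves after hearing the arm but before the interview has been randomised and has no interview covariates. The SAP's use of all available data with maximum likelihood deals with missing outcomes; a standard adjusted model still drops a record whose covariates are missing.

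**Working it through.** The documents give no figure on this point to reproduce. The check is a comparison of the sections, followed by an illustration.

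**Order of events**

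- Section 11, steps 1 to 3: randomise, then interview and urine, then handoff. Steps 4 and 5 continue in time order (week-1 call; 1, 3 and 6 months), so the numbering reads as a sequence.
- Section 24: consent, then envelope, then arm-specific procedures. This is compatible with the Section 11 order but silent on the interview.
- Sections 5 and 6: randomisation follows eligibility and consent. Neither makes it wait for baseline.
- Section 11 table: Intake stands before Onboarding (app training), but there is no row for randomisation.

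**Which measures are exposed**

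- Exposed, being self-reported: TLFB, pain, PTSD/trauma, HIV risk and self-reported service use.
- Little exposed: age, urine toxicology and record-based utilisation. The three stratifiers must be known before allocation.
- Exposed and also named as SAP covariates: mainly pain, trauma history and service use where it is self-reported. Anxiety is named, but the table lists no dedicated anxiety scale.

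**Illustration**

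The only input from the documents is 51 per arm (Protocol Section 25). The shift d and the slope b are assumptions.

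*Chance that the baseline test flags an arm-induced shift of d SD.* The standard error is sqrt(2/51) = 0.198. P = 1 − Φ(1.96 − d/0.198) + Φ(−1.96 − d/0.198).

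| d (SD) | P(flagged at p < .05) |
|---|---|
| 0 | 5% |
| 0.1 | 8% |
| 0.2 | 17% |
| 0.3 | 33% |
| 0.5 | 71% |

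*Movement of the adjusted effect.* In a linear model, the bias is −b × d, where b is the standardised covariate-outcome slope.

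| b | d = 0.1 | d = 0.2 | d = 0.3 | d = 0.5 |
|---|---|---|---|---|
| 0.3 | −0.03 | −0.06 | −0.09 | −0.15 |
| 0.5 | −0.05 | −0.10 | −0.15 | −0.25 |

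The size is therefore 0.03 to 0.25 SD, and zero when d = 0. In a change score (follow-up minus baseline) the whole shift carries over, as −d.

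*Loss between allocation and interview.* Each such participant is 1/102 = about 1% of the sample. The documents give no rate.

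**The case against.** The strongest reply is that no sentence says outright that the interview follows disclosure of the arm. A reader might take Section 24 as independent confirmation. It is not: it never mentions the interview, and randomisation after consent would still be true with an interview in between. The explicit order rests on the Section 11 list.

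Other parts leave the opposite order open. The Intake column includes the Mini Quiz, which Section 30 makes a check before enrolment, so some of Intake precedes randomisation. Stratifying on other substance use disorder also requires some history before allocation. The protocol refers to the grant for further procedural detail, and the order may be settled there. These points lower confidence, but none reverses the numbered list or holds allocation until baseline is complete.

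A second reply is that little is at stake. The primary outcomes, intake scheduled and intake completed, are binary and do not come from the baseline interview. The SAP's covariates are given as examples, and only a few are exposed. Patients unwilling to use the OARS+CM app if assigned are already excluded, which should limit early departures. This stands, and it confines the point to covariate-adjusted and change-score analyses. It does not remove the point, because the SAP plans both and assigns the primary outcomes to a generalised linear mixed model in which such covariates may be used.

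**Conclusion.** The stated order is the weaker of two equally feasible ones, and it should be changed. Followed as written, it lets knowledge of the arm reach self-reported baseline measures, of which pain, trauma history and service use are planned covariates.

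Three stronger conclusions are tempting, and the documents do not support them:

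- That baseline data are certainly recorded with the arm known. This is what the list implies, not something the protocol states.
- That the primary comparison is biased or intention to treat is broken. Unadjusted comparisons of scheduling and completion keep every randomised participant with an outcome and use no interview data.
- That a single bias figure can be quoted. The range of 0.03 to 0.25 SD depends on assumed shifts and slopes in a linear model for a continuous outcome. For the binary primary outcomes it is only indicative, and with no reporting shift the bias is zero.

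This is a worthwhile, nearly cost-free improvement, held with medium confidence because the full procedures may be set out in the grant.

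**What to change.** In Protocol Sections 11 and 24, state one order:

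1. Eligibility and consent.
2. Baseline interview and urine sample, completed and locked.
3. Opening of the allocation.
4. App training and handoff.

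Add a randomisation row or marker after Intake in the assessment table. Word step 3 to cover whichever mechanism is used, since Section 5 describes an urn procedure, Section 6 REDCap and Section 24 an envelope. If staff already interview first, the edit simply records current practice.

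The visit, staff and instruments stay the same. The one downside is that a few patients may complete the interview and leave before allocation. They would not have been randomised, so they would not enter the intent-to-treat sample.
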